1.4.4 Tacrolimus

Common adverse reactions to tacrolimus may be found in the package insert for tacrolimus and can include infection, malignancy, nephrotoxicity, hypertension, diabetes, neurotoxicity, and potassium imbalance (http://www.astellas.us/docs/prograf.pdf). Tacrolimus will be given for a finite duration (up through Day 60) and dose will be tapered after Day 46. Blood levels

of drug will be monitored throughout and doses adjusted accordingly to maintain levels between 3 and 7 ng/mL. Concomitant medications and food products will be monitored to avoid untoward interactions.

The tacrolimus regimen in this study is identical to that used in the previous thoracic SCI trial of AST-OPC1 (Geron Protocol CP35A007). There were no serious or unexpected adverse events related to tacrolimus in that study and all five subjects completed the course of tacrolimus per protocol. There were 16 adverse events reported as possibly related to immunosuppression with tacrolimus. These were all Grade 1 or Grade 2 in severity and were consistent with the common adverse reactions to tacrolimus including: nausea, urinary tract infection, and decreased magnesium blood level.

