7.4 Post-Injection Days 1-6

- Brief physical exam on Day 1
- Vital signs daily
- Hematology (as before) on Day 1
- Restart DVT prophylaxis on Day 1 (if applicable)
- Blood chemistry (as before) daily
- Tacrolimus blood level on Day 3 (+/- 1 day)
- Concomitant medications
- Adverse events

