7.6 Post-Injection Days 8-29

- Blood chemistry (as before) twice per week
- Tacrolimus blood level twice per week

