7.8 Post-Injection Days 31-59

- Blood chemistry (as before) once per week
- Tacrolimus blood level once per week
- Decrease tacrolimus dose by 50% (rounded to the nearest 0.5 mg, since this is the smallest capsule size available) on Day 46
- Decrease tacrolimus dose by another 50% (rounded to the nearest 0.5 mg) on Day 53; if the rounded total daily dose is 0.5 mg or lower, the subject will receive 0.5 mg once per day until tacrolimus is discontinued
- Concomitant medications
- Adverse events

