9.3.1 Safety Analyses

All reported adverse events will be coded to a preferred term and classified by System Organ Class using the current version of MedDRA. Adverse events will be listed by subject and will include preferred term, verbatim term, severity, seriousness, relationship, action taken, and outcome. Relationship will address attribution to the investigational product (AST-OPC1), the surgical procedure, and/or the immunosuppressive agent. Tabulations will be prepared for all adverse events, related events, Grade 3 and higher events, and serous events. Designated adverse events of special interest will be tabulated separately as appropriate.

Summary statistics of individual clinical laboratory parameters will be prepared by time period. Shift tables comparing baseline versus most abnormal value will be generated for selected analytes with standard toxicity grades. For selected laboratory analytes, the frequency of abnormal values and/or the incidence of Grades 3 and 4 values may be tabulated if appropriate.

Clinically significant changes in physical examination findings and ECGs will be presented descriptively. Vital signs will be summarized and listed by subject. Findings from immunological assessments will be presented appropriately.

Concomitant medications will be coded to generic term using the World Health Organization Drug Dictionary and will be tabulated across subjects and listed by subject.

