6.2.3 Clinical Laboratory Tests

Summary statistics (N, mean, standard deviation, median, minimum, and maximum) will be tabulated for chemistry, hematology, and liver function laboratory parameters during each period (Screening Visit, Baseline Visit, Post-Injection Days 1-6 Period, Day 7 Visit, Post-Injection Days 8-14 Period, Post-Injection Days 15-21 Period, Post-Injection Days 22-29 Period, Day 30 Visit, Post-Injection Days 31-37 Period, Post-Injection Days 38-44, Post-Injection Days 45-51 Period, Post-Injection Days 52-59 Period, Day 60 Visit, Day 90 Visit, and Day 180 Visit, and Day 365 Visit, as applicable by laboratory parameter) by cohort and overall. N will be calculated as the number of subjects with ≥1 assessment for the given parameter during the period. If a subject has >1 reading during a time period, the mean of the subject's results will be used for the calculation of the mean, SD, and median. For the

^{*}Subjects with >1 AE in respective category will only be counted once. For maximum severity tabulations, subjects will be counted once in the SOC and PT in the maximum severity.

minimum and maximum summary statistics, the minimum and maximum results taken during any assessment within cohort and overall during the time period will be used.

A table counting abnormal flags of the most abnormal value by time period will be generated for each cohort and overall. For each subject, the most abnormal value for a parameter will be taken as the maximum of the absolute value of (lab result – lower reference range) and the absolute value of (lab result – upper reference range) during the time period. At each visit, for each parameter, the number of subjects with low, normal, high, and clinically significant assessments will be tabulated.

Other samples taken, including immune response, xenotransplantation, blood culture, blood glucose, antibodies, and tacrolimus blood level measurement will be listed.

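### The laboratory flag tables keep one value per subject and period, so when several readings fall in a period the low, high and clinically significant counts can be short

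*SAP*

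**What the plan says.** SAP 6.2.3 plans this output: "A table counting abnormal flags of the most abnormal value by time period will be generated for each cohort and overall". The value that supplies the flag is chosen per subject, parameter and period: "the most abnormal value for a parameter will be taken as the maximum of the absolute value of" the difference between the result and each of the two reference limits. The paragraph ends by stating that, at each visit and for each parameter, "the number of subjects with low, normal, high, and clinically significant assessments will be tabulated". It does not say whether this last count uses only the selected value or every assessment in the period.

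The corresponding outputs in SAP Appendix 9.1 are the result-flag tables 14.3.4.1.2 (chemistry), 14.3.4.2.2 (hematology) and 14.3.4.3.2 (liver function).

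The protocol sets the number of readings that compete within a period:

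- Section 7.4, Days 1-6: "Blood chemistry (as before) daily"
- Section 7.6, Days 8-29: "Blood chemistry (as before) twice per week"
- Section 7.8, Days 31-59: "Blood chemistry (as before) once per week"

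Hematology is scheduled once in Days 1-6, on Day 1, and not at all in Days 8-29 or 31-59.

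**The concern.** A rule that keeps one value cannot show that a subject went out of range in both directions. Which direction survives depends on raw units. Results cannot fall below zero while highs have no ceiling, so for many parameters a low that is deep in proportion to its limit can be outranked by a high that is modest in proportion to its own. Clinical significance is tabulated but plays no part in the selection.

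Laboratory change is one of the three components of the primary safety endpoint (Protocol 9.2.1, SAP 4.1). Protocol 1.4.4 lists tacrolimus reactions that include "neurotoxicity, and potassium imbalance", an effect with no stated direction. The periods with most readings are those just after surgery and the start of tacrolimus. Neither SAP 6.2.3 nor Appendix 9.1 contains another cohort-level count of subjects with abnormal laboratory results, so these tables are where a reader would look for one.

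**Working it through.** **Inputs.** The rule and the periods are from SAP 6.2.3, and the reading frequencies from Protocol 7.1 to 7.13. The documents give no reference ranges, so every range and result below is an assumption chosen to show how the rule behaves. The plan states no figure to reproduce.

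**Step 1: what the rule measures.** Write L and U for the lower and upper limits and W = U − L. The score is max(|x − L|, |x − U|), which equals the distance from the range midpoint plus W/2. Hence:

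- x in range: score ≤ W
- x low: score = W + (L − x)
- x high: score = W + (x − U)

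Two results follow. With one two-sided range, an in-range value never outranks an out-of-range value. Between a low and a high, the larger raw excursion beyond its own limit is kept, so a low x is dropped when a high exceeds U + (L − x).

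**Step 2: low and high in the same period.**

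| Parameter (assumed range) | Low: distance below L; score | High: distance above U; score | Kept |
|---|---|---|---|
| Glucose (70-100) | 40: 30; 60 | 140: 40; 70 | high |
| Potassium (3.5-5.0) | 2.4: 1.1; 2.6 | 6.2: 1.2; 2.7 | high |
| Magnesium (1.7-2.3) | 0.9: 0.8; 1.4 | 3.2: 0.9; 1.5 | high |
| Phosphorus (2.5-4.5) | 1.0: 1.5; 3.5 | 6.2: 1.7; 3.7 | high |
| Sodium (135-145) | 120: 15; 25 | 150: 5; 15 | low |
| Calcium (8.5-10.5) | 6.5: 2.0; 4.0 | 11.5: 1.0; 3.0 | low |

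In every row one of two real abnormalities is left out of the flag count. Glucose shows the scale problem: 40/70 = 0.57 of the lower limit is dropped in favour of 140/100 = 1.4 times the upper limit. Any high above 70 + 30 = 130 would do the same, since U + (L − x) = 100 + (70 − 40) = 130. The potassium and magnesium pairs are near-ties and show only the loss of one direction.

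**Step 3: the floor at zero.** The largest possible low excursion is L, so any high above U + L hides every low. Under the assumed ranges that is 8.5 for potassium (8.5/5.0 = 1.70 × U), 170 for glucose (1.70 × U), 4.0 for magnesium (4.0/2.3 = 1.74 × U) and 7.0 for phosphorus (7.0/4.5 = 1.56 × U).

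**Step 4: clinical significance.** Suppose the glucose of 40 is flagged clinically significant and the 140 is not. The rule keeps 140, so the subject is missing from the clinically significant count as well as from the low count.

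**Step 5: where this can occur.** SAP 6.2.3 lists 16 periods. Scheduled chemistry readings are 6 in Days 1-6, about 2 in each of Days 8-14, 15-21 and 22-29, and about 1 in each of the other 12. That is 4 of 16 periods with more than one reading, holding 6 + 3 × 2 = 12 of 12 + 12 = 24 readings. Scheduled hematology has no such period. Unscheduled repeats would add to this if they enter the tables. SAP 5.3 assigns unscheduled data to the listings and does not say whether the tables include them.

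**Step 6: when even the any-abnormal count could fall.** Step 1 needs one complete range. If only an upper limit of 40 exists, an in-range 5 scores 35 and an abnormal 60 scores 20, so the normal value is kept. If two laboratories are used in one period, an in-range 38 (range 5-40) scores 33 and a high 36 (range 8-33) scores 28, with the same result. The documents do not show that either situation arises.

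**The case against.** A reader might infer that the flag tables undercount abnormal laboratory results in general. They do not. By Step 1, a subject with any out-of-range value is still counted as abnormal when one complete two-sided range applies. What can be short is the split between low and high, and the clinically significant count.

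A reader might also infer that severe lows are routinely hidden behind milder highs, or that the undercount is established. Neither is supported. The rule keeps the larger raw excursion, so milder is true only on a proportional or graded scale, and sodium and calcium show the low being kept. The loss needs one subject to go out of range both ways on one parameter, or to have a nearer clinically significant value, within one period. Protocol 1.4.4 does not describe each tacrolimus effect as two-directional: low magnesium and diabetes each point one way, and only the potassium effect is neutral.

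The data are also visible elsewhere. The summary minimum and maximum in SAP 6.2.3 use every assessment, and Appendix 9.1 includes by-subject laboratory tables and full listings. Protocol 10.1.1 and 10.3 can bring a clinically relevant abnormality into the adverse event tables. There were 25 treated subjects, no hypothesis test is planned, and the suspension rules use no laboratory counts. All of this stands and limits the weight of the point.

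The remaining defence is that the closing sentence of the paragraph may count every assessment, in which case nothing is lost. But the selection rule would then have no function, and the sentence announcing a table of flags of the selected value would be wrong. Two programmers could build different tables, so the text needs correcting on either reading.

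Protocol 9.3.1 promised this: "Shift tables comparing baseline versus most abnormal value will be generated for selected analytes with standard toxicity grades". It does not settle the matter, since it too uses a single most abnormal value. The absence of those shift tables from the SAP is a separate question.

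**Conclusion.** The point holds in limited form and is minor. Followed as written, SAP 6.2.3 can give short counts of subjects with low, high and clinically significant values. For scheduled tests this concerns chemistry in 4 of 16 periods (Days 1-6, 8-14, 15-21 and 22-29) and no hematology period. The algebra rests only on the stated rule. The worked pairs rest on assumed ranges and values, and the reading counts assume adherence to the schedule. The documents give no basis for estimating how often a flag would be lost. Only descriptive tables are affected, and the dropped results stay in the by-subject tables and listings. The reasons to correct it are that the tables summarise a primary safety component and that the correction is simple.

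**What to change.** In SAP 6.2.3 and Tables 14.3.4.1.2, 14.3.4.2.2 and 14.3.4.3.2:

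- For each period, and over all assessments in it, count separately the subjects with at least one low value, at least one high value and at least one clinically significant value.
- Allow a subject to appear in more than one column.
- Define normal as all values in range.
- Delete the single-value distance rule.
- State whether unscheduled repeats are included.

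If each result is flagged against its own laboratory's range, this also removes the one-sided and mixed-range cases in Step 6. The cost is one SAP paragraph, a table footnote and a small programming change, with no new data. The drawback is that the columns no longer sum to N, which the footnote should say. SAP 5.4 has every table produced at the interim as well as at the end, so one change serves both.

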6.2.4 Magnetic Resonance Imaging (MRI)

All study-driven MRI reading will be performed by a central group of neuroradiologists with extensive experience in MRI evaluation of spinal cord trauma. The screening/baseline MRI will be used for eligibility and to make a preliminary determination of the target site for AST-OPC1 injection. Following AST-OPC1 injection, the MRI images will be assessed according to standard practice and with specific attention to the following potential risks:

- intramedullary hemorrhage, CSF leak, epidural abscess, infection
- evidence of expanding cyst or mass at the injection site or elsewhere in CNS
- evidence of inflammatory lesion(s) at injection site or elsewhere in CNS
- evidence of CSF flow obstruction

Several additional parameters may be measured for future research analyses. These may include:

- Length of contusion (i.e., maximal extent of petechial hemorrhages)
- Presence/absence of intramedullary hemorrhage
- Length of intramedullary hemorrhage
- · Length of edema
- Percent compression at epicenter

An MRI listing will be produced from the central reader data. All MRI data will be assessed qualitatively.

6.2.5 Vital Signs

Summary statistics (N, mean, standard deviation, median, minimum, and maximum) will be tabulated for vital sign parameters during each period by cohort and overall. N will be calculated as the number of subjects with ≥1 assessment for the given parameter during the period. If a subject has >1 reading during a time period, the mean of the subject's results will be used for the calculation of the mean, SD, and median. For the minimum and maximum

summary statistics, the minimum and maximum results taken during any assessment within cohort and overall during the time period will be used.

6.2.6 Physical Exam

The number and percentage of subjects with normal, abnormal non-clinically significant, and abnormal clinically significant physical exam results at the Screening visit will be tabulated by parameter for each cohort and overall. For visits after the Screening visit, no change, non-clinically significant change, and clinically significant change will be tabulated at each visit by parameter for each cohort and overall.

Neurological examination results will be listed.

6.2.7 Electrocardiogram

The number and percentage of subjects with normal, abnormal non-clinically significant and abnormal clinically significant electrocardiogram readings at Screening and the 1 Week visit will be tabulated.

6.2.8 International Spinal Cord Injury Pain Basic Data Set

Pain will be assessed using the International Spinal Cord Injury Pain Basic Data Set Data Collection Form Version 2.0. All pain data will be listed.

Neuropathic pain will be summarized by cohort and overall as follows:

- The number and percentage of subjects that report ≥1 neuropathic pain at each visit
- The number and percentage of subjects that report ≥1 at-SCI-level neuropathic pain at each visit
- The number and percentage of subjects that report ≥1 below-SCI-level neuropathic pain at each visit
- Summary statistics of the average neuropathic pain intensity reported at each visit. If a subject reports > 1 neuropathic pain at a visit, the mean intensity for the subject will be used when calculating the summary statistics.

6.3 Efficacy Analyses

All efficacy data will be listed for all subjects. Efficacy summaries will be presented for the Intent to Treat Population.

6.3.1 ISNCSCI

ISNCSCI score data of Sensory Score, Neurological Sensory and Motor Scores, Neurological level, ASIA Impairment Scale and Zone of Partial Preservation (ZPP) levels will be listed for

each ISNCSCI examination completed at the Screening Visit, Day 7 Visit, Day 30 Visit, Day 60 Visit, Day 90 Visit, Day 180 Visit, Day 270 Visit and Day 365 Visit. Results of the ISNCSCI Sensory Scores, Motor Scores, Neurological Level and Zone of Partial Preservation (ZPP), and Anorectal Examination will be presented in listings.

Baseline for the ISNCSCI assessment will be defined as the Baseline Visit on Day -2 or Day -1.

Upper Extremity Motor Score (0-50) and change from baseline will be summarized with N, mean, standard deviation, 95% confidence interval, median, minimum, and maximum by for the overall Intent to Treat population. A positive change is considered improvement and a negative change is considered worsening.

Motor and sensory level at each visit and changes in motor/sensory level from baseline will be defined as:

Change in Level = the number of levels the motor/sensory level has changed from baseline visit, where a positive number represents a change in the caudal direction and a negative number represents a change in the rostral direction. A change in the caudal direction is considered improvement while a change in the rostral direction is considered worsening.

The change in motor and sensory level will be tabulated as follows:

- Percentage of subjects with an ascending motor level on either side of the body relative to baseline
- Percentage of subjects with no motor level change on either side of the body relative to baseline
- Percentage of subjects with one motor level improvement on at least one side of the body relative to baseline
- Percentage of subjects with one motor level improvement on both sides of the body relative to baseline
- Percentage of subjects with a two or more motor level improvement on at least one side of the body relative to baseline

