6.4 AST-OPC1 Administration

One day prior to the planned injection of AST-OPC1 (i.e., Day –1), subjects should have any ongoing pharmacological DVT prophylaxis suspended in preparation for surgery. These may be restarted on Day 1.

Surgery to inject AST-OPC1 must be delayed if the subject has a temperature \geq 38.6°C at any 2 time points between Day –1 and Injection Day prior to surgery. Depending upon the duration of the delay of treatment, the Medical Monitor may request that certain baseline tests be repeated.

On Injection Day subjects will receive the dose of AST-OPC1 as determined by cohort assignment (Table 6-1). AST-OPC1 may only be administered by a licensed surgeon who has both training and experience in performing intradural surgical procedures on the spine. In addition, each surgeon must be trained and qualified by the Sponsor on the use of the SPD and the injection procedure prior to their first administration of AST-OPC1 (see Appendix C).

Cohort	Dose (# of cells)	Concentration (cells/µL)	Volume per Injection (µL)	Number of Injections	Total Volume Administered (μL)
1	2 x 10 ⁶	4 x 10 ⁴	50	1	50
2	1 x 10 ⁷	2 x 10⁵	50	1	50
3	2 x 10 ⁷	2 x 10⁵	50	2	100
4	1 x 10 ⁷	2 x 10⁵	50	1	50
5	2 x 10 ⁷	2 x 10⁵	50	2	100

 Table 6-1:
 AST-OPC1 Dose Cohorts and Injection Preparation

The injection procedure requires an open or minimal-access surgical exposure from a posterior approach with the subject sedated under general endotracheal anesthesia. Neuromuscular paralyzing agents will also be administered to prevent subject movement during the injection procedure. This is necessary because if a subject moves while the needle is in the spinal cord, additional damage to the adjacent spared spinal cord tissue could occur.

It is recommended that the surgeon and anesthesiologist consider the placement of an arterial line for intraoperative blood pressure monitoring, since this could facilitate rapid detection and management of an episode of intraoperative autonomic dysreflexia. For subjects with incomplete SCI (i.e., AIS-B), intraoperative monitoring of somatosensory evoked potentials is recommended to determine whether these are adversely affected by the injection procedure.

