7.2 Baseline (Days –2 to –1)

Note: As indicated below, some of the baseline assessments may be performed as early as

Day -4 if required to accommodate clinical site staff availability.

- Brief physical exam and vital signs (check vital signs both days)
- Standard neurological exam (may be performed on Day -4 to -1)
- ISNCSCI exam (may be performed on Day -3 to -1, unless the screening ISNCSCI was performed on Day -3.)
- Partial Graded Redefined Assessment of Strength, Sensibility and Prehension (GRASSP; may be performed on Day -4 to -1)
- Spinal Cord Independence Measure (SCIM; may be performed on Day -4 to -1)
- Hematology (as before)
- Blood chemistry (as before)
- Fasting blood glucose (may be done pre-op on injection day)
- Blood for HLA typing (may be obtained on Day -4 to -1)
- Blood for immune response monitoring (may be obtained on Day -4 to -1)
- Blood for xenotransplantation archival (may be obtained on Day -4 to -1)
- Withhold pharmacological DVT prophylaxis on Day -1
- Concomitant medications
- Adverse events

If the day of injection is delayed, some or all of the following tests and procedures may need to be repeated prior to the new Injection Day. The determination of which tests and procedures to be repeated will be made by the Investigator after consultation with the Sponsor's Medical Monitor.

Note: baseline tests and procedures that are not repeated will still be deemed to have been collected within the appropriate pre-operative window.

- Brief physical exam and vital signs
- Brief ISNCSCI exam
- MRI (cervical spine, non-contrast only)
- Hematology (as before)
- Blood chemistry (as before)
- Concomitant medications
- Adverse events

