4.4.2 Baseline and Change from Baseline

Unless indicated otherwise, change from baseline (CFB) will be calculated as follows, where the baseline assessment is the last assessment before AST-OPC1 injection:

• CFB = Value at Visit - Baseline

Percent change from baseline (PCFB) will be calculated as follow:

• PCFB (%) = 100*(Value at Visit - Baseline)/Baseline

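### If the injection is delayed, does the SAP need a new rule for which ISNCSCI exam is the baseline?

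*SAP*

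**What the plan says.** SAP 6.3.1 fixes the ISNCSCI baseline: "Baseline for the ISNCSCI assessment will be defined as the Baseline Visit on Day -2 or Day -1". It defines change in level as "the number of levels the motor/sensory level has changed from baseline visit". The general definition in SAP 4.4.2 is that "the baseline assessment is the last assessment before AST-OPC1 injection", but that section gives way wherever a more specific definition is stated.

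Protocol 7.2, under its Baseline heading, gives the full exam some latitude: "ISNCSCI exam (may be performed on Day -3 to -1, unless the screening ISNCSCI was performed on Day -3". It then covers a postponed injection. The tests that may be repeated include a "Brief ISNCSCI exam". On who decides: "The determination of which tests and procedures to be repeated will be made by the Investigator after consultation with the Sponsor's Medical Monitor". On anything left un-repeated: "baseline tests and procedures that are not repeated will still be deemed to have been collected within the appropriate pre-operative window". Protocol 6.4, which postpones surgery for fever, adds: "Depending upon the duration of the delay of treatment, the Medical Monitor may request that certain baseline tests be repeated".

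The SAP does not mention a delayed injection. The shortened exam is named once and described nowhere in the documents supplied. Protocol Appendix D describes only the full exam, with 10 key muscles and 28 sensory regions on each side.

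**The concern.** Upper extremity motor score and motor level are the secondary endpoint measures, and both are summarised as change from baseline in one pooled set with no concurrent control. The choice of baseline exam therefore feeds directly into the reported change.

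Two things could go wrong after a delay. First, a shortened exam might displace a complete one. If it left out sensory testing, it would give no sensory level. It would also give no motor level where C5 is below grade 3, because Appendix D then takes the motor level from the sensory level. SAP 5.3 does not impute, so the subject would drop out of the change summary. Second, an old exam might stand as baseline. Protocol 1.3.3 says spontaneous recovery begins to plateau only at about 6 months, so recovery between the exam and the injection would be counted as change after treatment. GRASSP and SCIM are not on the repeat list at all.

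**Working it through.** Neither document states an exam age, so there is no figure to reproduce. The check asks which exam the SAP picks, and how old an un-repeated exam could be.

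**Which rule governs.** SAP 4.4.2 yields to 6.3.1, so the last-assessment rule does not decide the ISNCSCI case. SAP 6.3.1 can be read in two ways, because SAP 4.4.1 counts Study Day from the actual injection date.

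| After a delay | 6.3.1 read by Study Day | 6.3.1 read by visit |
|---|---|---|
| Repeat on new Day -2 or -1 | shortened exam (both exams qualify if a Day -1 exam is followed by a 1-day delay) | full baseline exam |
| Repeat on new Day -3 | neither, so missing | full baseline exam |
| No repeat | missing once the full exam falls on Study Day -3 or earlier | full baseline exam |

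This was checked for delays of 1, 2, 5 and 21 days, a full exam planned for Day -1, -2 or -3, and a repeat on new Day -1, -2, -3 or not at all. The by-visit column is constant because a visit label does not move with the injection date. It assumes that the repeat is not entered as the Baseline Visit exam, a point on which the documents are silent.

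**Which reading fits.**
- Protocol 7.2 places a Day -3 exam under its Baseline heading. A strict day count would discard that permitted exam even with no delay.
- SAP 6.3.1 measures change in level from the visit.
- Protocol 7.2 treats un-repeated exams as in window.

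All three points favour the visit reading.

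**Oldest un-repeated exam.** Age = (latest dosing day - earliest planned dosing day) + days from exam to planned injection.
- 21-42 day window, Day -3 exam: (42 - 21) + 3 = 24 days (23 from Day -2, 22 from Day -1).
- 14-30 day window, same Day -3 allowance assumed: (30 - 14) + 3 = 19 days.
- The Amendment 3 rationale counts 17 subjects already dosed, and SAP 3.2.1 gives 25 in total. At most about 25 - 17 = 8 fall under the later window.

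**Share of the baseline-to-visit interval that precedes injection.** Share = age / (age + visit day).
- Age 24: Day 30, 24/54 = 44%; Day 365, 24/389 = 6%.
- Age 19: Day 30, 19/49 = 39%; Day 365, 19/384 = 5%.

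These are shares of calendar time, not of recovery.

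**Weight of one subject.** The efficacy set is 6 + 6 + 6 + 4 = 22, so one subject moves a motor-level percentage by 1/22 = 4.5 points.

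**Motor level that depends on sensory testing.** A neurological level of C5 or below implies C5 of at least grade 3, so this mainly concerns C4 subjects. Amendment 3 first admitted them, so they number at most 8 of 22 (36%), and only if every later subject was C4.

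**Would a rule change the result?** If nothing was repeated, the alternatives to the baseline exam are the older screening exam or no baseline, so a sensible rule keeps the exam the visit reading already keeps. If the repeat lacks a component, the endpoint cannot be scored from it and the analyst returns to the full exam. A choice remains only if the repeat is complete. Either exam is then usable, and they differ in age by the gap between them.

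**The case for a change.** The strongest case for a change is that two programmers could follow the text and derive different baselines. One would count Study Days, the other would use the visit. The endpoint is secondary, the set is small and uncontrolled, and one subject is worth 4.5 points. The SAP also treats uneven baselines as material elsewhere: in 6.3.5 it drops change from baseline for Qualitative Prehension because the baseline visit differed across amendments. One sentence would remove the doubt.

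Part of this stands. The shortened exam is undefined, the SAP is silent on delay, and no planned table flags an old baseline exam. A literal day count would give odd results.

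The rest is weaker. The day count conflicts with the protocol's own early window, and it would leave a baseline missing for a subject with a complete pre-injection exam on file. The loss of a sensory or motor level supposes that the shortened exam omits sensory testing, which nothing in the documents says; the eCRF casebook cited by the SAP was not available and may define it. The 24-day age needs four things together: dosing planned for day 21, an exam on Day -3, actual dosing on day 42, and no repeat. Protocol 6.4 ties repeat requests to the length of the delay, which makes that combination less likely. Old exams would not be hidden either. SAP section 6 puts all eCRF data for all subjects and visits into listings, and 5.3 adds unscheduled visits, although the visit list in 6.3.1 omits the Baseline Visit.

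**Conclusion.** No change to the plan is needed. After a delayed injection the wording of SAP 6.3.1 is ambiguous, but the reading that agrees with the protocol keeps the full baseline exam, and that is what an analyst would use. An un-repeated exam could be at most 24 days old for about 8 subjects and 19 days for the others. At Day 365 that is some 5-6% of the interval from baseline. At Day 30 the worst-case share is larger, at 39-44%, but no SAP rule can supply a newer exam where none was done.

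This conclusion assumes that a repeat exam can be told apart from the full Baseline Visit exam in the data, and that listings carry exam dates as SAP section 6 says. The number of delayed injections and the content of the shortened exam are unknown. If there were no delays, the point has no effect. If shortened exams were complete, no level is lost and only the choice between two usable exams remains. With descriptive summaries of 22 subjects and no hypothesis tests, this is a programming detail to settle when the baseline is derived.
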